5.1.2 Arm B (Lenalidomide + Epoetin Alfa)

Lenalidomide 10 mg po/day on days 1-21 followed by 7 days of no therapy and epoetin alfa 60,000 units subcutaneously (s.c.) every week. Repeat cycles every 28 days for a total of 4 cycles. (Refer to Section [5.1.3](#) for further treatment).

Blood pressure and heart rate measurements will be assessed prior to each dose of epoetin alfa.

Patients with a pretreatment platelet count of 50,000-99,000/mcL or an ANC of 500-999/mcL will receive a lenalidomide dose of 5 mg po/day on days 1-21.

5.1.3 Patients on Arm A or Arm B who achieve a Major Erythroid Response (MER) according to modified International Working Group (IWG) criteria described in Section [6](#) may continue the assigned treatment in the absence of limiting toxicity or disease progression.

Patients on Arm A who do not achieve a MER will have the option to cross over to Arm B (see Section [5.2](#)). If they choose not to cross over, they will then discontinue protocol treatment.

Patients on Arm B who do not achieve a MER will discontinue treatment.

If the treating MD and/or PI feels that the subject is receiving benefit from study (in the way of decreasing RBC transfusion frequency and/or HGB increase outside RBC transfusion influence) but does not meet MER, subjects may remain on treatment if they have achieved a **minor** erythroid response until demonstrating signs of lack of continued response (example: increase in RBC transfusion dependence, or decreased HGB on consistent basis outside of the influence of RBC transfusions). See Section [6.1.2.3](#) for reference. If there are questions regarding this item, please have the treating MD and/or PI email [name] for further discussion on a case by case basis.

Treatment with white cell growth factors is allowed for the management of neutropenia at the discretion of the treating investigator.

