5.2 Cross-Over Treatment

Patients who fail to achieve a MER on Arm A AND patients on Arm A who relapse will be offered to cross over to Arm B to receive combined treatment in the absence of limiting toxicity precluding continuation of lenalidomide treatment. The dose for Arm B crossover is the dose of lenalidomide that would otherwise be implemented for continuation of therapy according to Section [5.5](#). If a patient does not choose to cross over, he/she will then discontinue study treatment.

Response to cross-over treatment will be assessed after 16 weeks (4 cycles) of combined therapy (i.e., study week 32). Arm A patients that cross over to Arm B that do not achieve a MER after 16 weeks of combined treatment (i.e. week 32) will discontinue protocol treatment.

Rev. 6/14

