9.3 Secondary Objectives

All analyses on secondary endpoints will be performed on 212 patients randomized before May 19, 2010 and after September 24. The 14 patients (7 on arm A; 7 on arm B) randomized between May 19, 2010 and September 24, 2010 will be excluded.

Time to MER is defined in responders as the time from randomization to the documented date of MER. For transfusion independent patients, the date of MER is the first date of the elevation in hemoglobin level of more than 2 g/dL that has been sustained for at least 8 weeks. For transfusion dependent patients, the date of MER is the beginning date of the time interval of transfusion independence that has been sustained for at least eight weeks.

Time to MER will be compared between lenalidomide monotherapy and combined treatment of lenalidomide and epoetin alfa in MER responders, using a one-sided log-rank test at the significance level of 0.025. Data from a prior study, MDS-001, of patients with MDS show that the median to MER is 11.5 weeks for patients on the lenalidomide schedule of 10 mg/day for 21 days (10). Under the assumption that the proportions of major erythroid responders are 30% for the monotherapy and 50% for the combined therapy, the log-rank test will have 80% power to detect a hazard ratio of 1.88 of the combined therapy over the

monotherapy. If time to MER follows an exponential distribution, this difference corresponds to an improvement in median time to MER from 11.5 weeks to 6.1 weeks.

Duration of MER response is defined as the time interval between the documented date of MER and the earliest date of resumption of RBC transfusions ≥ 2 units in an 8 week period, a reduction in hemoglobin concentration ≥ 2 g/dL in the absence of acute infection, gastrointestinal bleeding and hemolysis, or death.

Duration of MER response will be summarized by Kaplan-Meier method for patients who achieve MER by treatment arms. A secondary analysis will be done on duration of MER response by excluding all patients on arm B whose epoetin alfa treatment was interrupted by the drug supply issue occurred in September 2010.

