The 90% confidence interval of the rate of MER to salvage combination therapy will be computed in patients who fail to achieve an MER with lenalidomide monotherapy and cross over to the combination therapy. Since it is assumed that the MER rate on the monotherapy arm is 30%, 74 patients from the monotherapy arm will fail to achieve MER. If among them 60 patients cross over to the combination therapy arm, the 90% confidence interval of the MER rate of the 60 patients will be no wider than 22.5%. A secondary analysis will be done on the rate of MER to salvage combination therapy by excluding those cross over patients whose epoetin alfa treatment was interrupted by the drug supply issue occurred in September 2010.

The minor erythroid response rate will be compared between treatment arms by Fisher's exact test. In a prior study MDS-001 of patients with MDS, 2 minor erythroid responses were observed from 17 patients who were on the lenalidomide schedule of 10 mg/day for 21 days (10). If the minor erythroid response rate is 10% for the monotherapy arm and 30% for the combination therapy arm, there is 94% power to detect this difference at a two-sided significance level 0.05.

Cytogenetic response rate will be calculated by treatment arm among patients with cytogenetic abnormalities, along with its 90% confidence interval. If 45% of patients are expected to have genetic abnormalities, the 90% confidence interval of the response rate is no wider than 25.6% for each arm.

Bone marrow response (CR+PR) rate and its 90% Confidence Interval will be calculated by treatment arm. The 90% Confidence Interval of the bone marrow response rate is no wider than 16.8% for each arm.

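### The supply-gap analysis of MER duration drops Arm B responders because they were still on epoetin alfa, which shortens Arm B duration; the salvage analysis has a smaller form of the same fault

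*Combined protocol and SAP*

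**What the plan says.** Section 9 states that epoetin alfa was held on September 24, 2010 and was available again on October 27, 2010. At the hold, 57 patients had been randomized (29 on Arm A, 28 on Arm B), and 7 Arm B patients were still in their first 16 weeks.

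Section 9.3 first applies a symmetric exclusion by randomization date to all secondary endpoints: "The 14 patients (7 on arm A; 7 on arm B) randomized between May 19, 2010 and September 24, 2010 will be excluded".

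The main duration analysis is descriptive: "Duration of MER response will be summarized by Kaplan-Meier method for patients who achieve MER by treatment arms". A further duration analysis is then planned, "by excluding all patients on arm B whose epoetin alfa treatment was interrupted by the drug supply issue" of September 2010. No corresponding rule is given for Arm A.

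For salvage, the main analysis is the MER rate with a 90% confidence interval among Arm A patients who failed monotherapy and crossed over. A further analysis is planned, "excluding those cross over patients whose epoetin alfa treatment was interrupted by the drug supply issue occurred in September 2010".

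Two treatment rules decide who could be on epoetin alfa at the hold. Section 5.1.3 says "Patients on Arm B who do not achieve a MER will discontinue treatment", although patients with a minor response may stay on treatment. Section 5.2 says that crossover patients who "do not achieve a MER after 16 weeks of combined treatment (i.e. week 32) will discontinue protocol treatment".

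**The concern.** Both further analyses select patients by a state reached after randomization: being on epoetin alfa on one calendar day. Under the continuation rules, that state depends on response. For duration, removing patients because their response was still running is selection on the outcome. It is applied to one arm only, although duration is summarized by arm.

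These are the only planned supply-gap checks for objectives 2.2.2 (duration) and 2.2.3 (salvage MER). A reader would use them to judge whether the interruption affected the main results. A shorter Arm B duration could be read as a treatment finding when the exclusion rule produced it.

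**Working it through.** **1. The plan's own figure.** Expected Arm A non-responders: 106 × 0.70 = 74.2, matching the stated 74. The largest exact (Clopper-Pearson) 90% interval width for n = 60 is 22.52%, matching the stated 22.5%. The plan gives no figures for the two supply-gap analyses, so the rest rests on stated assumptions.

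**2. Who was interrupted on Arm B.** May 19 to September 24, 2010 is 128 days, or 18.3 weeks. Arm B patients left after the symmetric exclusion were randomized at least that long before the hold, so they were essentially all past week 16. The 7 Arm B patients counted as within 16 weeks equal in number the 7 Arm B patients excluded. After week 16, non-MER patients stop. Minor responders may continue but are not in the MER duration set. Within that set, interrupted essentially means still responding.

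**3. How many.** Early Arm B patients: 28 − 7 = 21. Expected responders at 50%: 10.5. All Arm B responders: 106 × 0.50 = 53.

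**4. Effect on the Arm B median if the gap ended no response.** Assumptions not in the plan: exponential durations, and early patients entering over 50 or 70 weeks before May 19, 2010. Simulated Kaplan-Meier medians in weeks:

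| Assumed median | Entry period | Mean number dropped | All kept, no gap | Exclusion as planned | Censored at hold |
|---|---|---|---|---|---|
| 26 | 50 / 70 | 3.8 / 3.1 | 25.8 / 25.8 | 24.2 / 24.5 | 25.8 / 25.9 |
| 52 | 50 / 70 | 6.7 / 5.8 | 52.0 / 51.9 | 47.5 / 47.1 | 52.5 / 52.1 |
| 81 | 50 / 70 | 8.0 / 7.4 | 82.1 / 80.9 | 76.5 / 73.4 | 82.2 / 81.7 |
| 104 | 50 / 70 | 8.4 / 8.0 | 105.2 / 105.8 | 97.5 / 96.0 | 103.6 / 105.7 |

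The falls run from 5.0% (25.8 to 24.5) to 9.3% (80.9 to 73.4). Separate runs with 10 early responders and entry over 40 or 70 weeks give 53.5 to 47.7 and 53.6 to 47.6, about 11%. The range used is therefore 5-11%. The only duration figure in the plan is the MDS-001 median in section 1.2, not reached (81+ weeks).

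**5. If the gap ended responses.** Assume half of the interrupted responders lost response. The main analysis is then itself shortened (entry over 50 / 70 weeks):

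| Assumed median | Main analysis | Exclusion | Censored at hold |
|---|---|---|---|
| 52 | 48.2 / 49.3 | 46.4 / 46.9 | 52.1 / 52.3 |
| 81 | 69.7 / 73.1 | 76.3 / 74.0 | 82.0 / 81.9 |

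Exclusion lies below the main result in the first row and above it in the second. Censoring at the hold stays close to the assumed median in both.

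**6. Salvage.** The May 19 cut-off is by randomization date, so it does not remove crossovers in their first 16 weeks of combination. Early Arm A patients: 29 − 7 = 22. Expected crossovers among them: 22 × 0.70 × 60/74 = 12.5, assuming crossover at week 16.

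- *First 16 weeks of combination at the hold* (randomized 18.3 to 32 weeks before it): E = 12.5 × 13.7/50 = 3.4, or 12.5 × 13.7/70 = 2.4. These are dropped without selection on response.
- *Past the assessment and still responding*, with an assumed 52-week median salvage duration: the mean fraction still responding is (1 − e^−x)/x with x = ln 2 × (L − 13.7)/52, where L is the entry period. This is 0.79 for L = 50 and 0.70 for L = 70. At a salvage rate p of 30%, R = 9.1 × 0.30 × 0.79 = 2.2, or 10.0 × 0.30 × 0.70 = 2.1. At the pilot's MER rate of 3/18, R = 1.2 in both cases.
- *Rate after exclusion* = (60p − Ep − R)/(60 − E − R). For p = 30%, L = 50: (18 − 1.03 − 2.16)/(60 − 3.42 − 2.16) = 14.8/54.4 = 27.2%. For p = 3/18: (10 − 0.57 − 1.20)/(60 − 3.42 − 1.20) = 8.23/55.4 = 14.9%. If only 60% of the early failures cross over, the results are about 28% and 15.4%.
- *Exclusion by date*: (60p − Ep)/(60 − E) = p, so the rate does not move.

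**The case against.** The best defence is that the stakes are small. The main analyses keep these patients, duration has no test, objective 2.2.2 asks to evaluate rather than compare, and no decision rule uses either result. All of that stands and limits the severity.

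The match between interrupted and still responding is also close rather than exact. Under section 5.5.5 epoetin alfa can be withheld for a high hemoglobin, and such a patient was arguably not interrupted by supply. Responders off treatment for toxicity are still followed for response (section 5.8). Both would stay in, so the numbers dropped in step 4 are nearer an upper bound.

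Three stronger readings are tempting but not supported:

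- A reader might infer that the exclusion does more harm than the gap. The documents give neither the number interrupted nor how many lost response. Step 5 shows that exclusion can be nearer the truth than the main analysis.
- A reader might carry the duration argument over to salvage and infer that those dropped are mostly ongoing responders. In step 6, settled responders are only 26-46% of those dropped at salvage rates of 17-30%, and pass half (51-59%) only at 50%. The salvage analysis also has no comparator arm, so a bias between arms cannot arise there.
- A reader might illustrate salvage by taking three responders from 17/60, leaving 14/57 (28% to 25%). That drops no non-responders, and 28% is the pilot's rate of any erythroid response (5/18). Its MER rate was 3/18, or 17%.

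**Conclusion.** The duration point holds. The further analysis selects on ongoing response in Arm B only, and nothing else in the plan repairs this. Relative to uninterrupted treatment it understates the Arm B median by roughly 5-11%. The direction follows from the plan's own rules. The size rests on assumed exponential durations, an assumed entry pattern and a 50% response rate among 21 early patients. The direction relative to the main analysis is not determined.

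The salvage point holds in a narrower form. Crossovers past their 16-week combination assessment had their outcome settled before the gap. Dropping those still responding, while non-responders who had stopped stay in, corrects nothing and lowers the rate by about 2-3 points. That is small beside a planned interval up to 22.5 points wide. Crossovers still in their first 16 weeks are also dropped, but without selection on response.

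Severity is minor: both are supplementary analyses of secondary endpoints, and the primary endpoint is unaffected.

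**What to change.** Replace two sentences in section 9.3.

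- **Duration:** keep every MER responder in the set and censor affected Arm B patients at September 24, 2010. As a check, repeat with the same calendar censoring in Arm A.
- **Salvage:** exclude every crossover patient whose 16-week combination assessment period overlaps September 24 to October 27, 2010, whatever the outcome, and keep all others.

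Report how many patients each rule affects. The cost is slightly more censoring in the duration analysis. The rules need only the response and crossover dates that these analyses already require.

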9.4 Interim Analyses

All interim analyses will be performed on patients randomized before May 19, 2010 and after September 24. The 14 patients (7 on arm A; 7 on arm B) randomized between May 19, 2010 and September 24, 2010 will be excluded.

The interim analyses will be conducted every six months, in conjunction with scheduled ECOG-ACRIN DMC meetings, starting at 25% information time, unless small increments of information ($<10\%$) are gained during six months. Taking the delay of the initiation of accrual and the study suspension into account, the first and final analyses are anticipated to take place at

approximately 2.5 and 5.5 years after the study begins active accrual. The formal interim analyses will be conducted using the truncated O'Brien Fleming group sequential boundaries as described in Freidlin et.al. (1999).

Table 1 summarizes the operating characteristics of this design. For example, this trial can be stopped early at the fourth interim analysis (63% information time) in favor of an alternative hypothesis of adding lenalidomide to epoetin alfa improves the MER rate if the standardized test statistic comparing two MER rates is greater than 2.6523.

Table 1: Operating Characteristics

Analysis	Information Time	Eligible Cases for Two Arms	Upper Boundary	Nominal Significance level
1	0.25	53	3.2905	0.0005
2	0.38	80	3.2905	0.0005
3	0.51	108	3.0606	0.0011
4	0.63	133	2.6523	0.004
5	0.75	159	2.4101	0.008
6	0.88	186	2.2094	0.014
7	1.00	212	2.0703	0.019

Since lenalidomide in combination with epoetin alfa might not significantly improve the MER rate compared to lenalidomide alone, this study will be monitored for early stopping in favor of null hypothesis. Using repeated confidence interval methodology similar to that described by Jennison and Turnbull, at each interim analysis, a nominal $1-\alpha$ confidence interval on the difference in MER rates will be computed using the nominal one-sided significance level of the use function boundary at the information fraction at the particular analysis time. The results will be provided to the DMC as a guideline to use when evaluating the study. If the confidence interval does not contain the alternative of interest, 20%, consideration may be given to early termination of the study.

9.4.1 Early Stopping for Excessive Toxicity

All toxicities will be monitored closely and reported using ECOG-ACRIN's standard AE mechanism. Since the proposed regimen of lenalidomide or lenalidomide + epoetin alfa has not been examined in a cooperative group setting, the tolerability of these regimens will be initially tested in the first 30 patients in Arm A and Arm B. We will consider each regimen tolerable if the grade 3 or higher thrombo-embolic events is 1% or less, and intolerable if the rate is 10% or higher. In addition to thrombo-embolic events, we will consider each regimen tolerable if the grade 3 or higher regimen related other toxicity rate is 30% or less, and intolerable if the rate is 50% or greater with proper dose adjustment. Hematologic toxicities are expected effects of the regimens and therefore will not be considered in the stopping rule. If, in the first 30 patients treated in Arm A or Arm B, we observe 2 or more patients with grade 3 or higher thrombo-embolic events, or 13 or more patients with grade 3 or higher related other toxicity after proper dose adjustment, the study will be terminated to further accrual. Assuming statistical independence of occurrence of thrombo-embolic events and other regimen related toxicities, with this

design, the probability of terminating the study early is 0.12 if the true but unknown rate of grade 3 or higher thrombo-embolic events is 1% and the true but unknown rate of grade 3 or higher other toxicity is 30%; the probability of terminating the study early is at least 0.83 if the true but unknown rate of grade 3 or higher thrombo-embolic events is 10% or the true but unknown rate of grade 3 or higher other toxicity is 50%. If the study does not meet those toxicity early stopping rules after the first 30 patients in arm B, additional 9 patients on arm B will be closely monitored for grade 3 or higher thrombo-embolic and other regimen related toxicities and the results will be reported to DMC.

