1.3 Toxicity Profile

Clinical trials performed to date indicate that lenalidomide has encouraging erythropoietic activity in lower risk MDS with poor rhu-erythropoietin response profile. Although response rate is moderate in patients with non-del 5q31 karyotypes, erythropoietic activity may be improved by the addition of epoetin alfa, given the erythropoietin-dependence of lenalidomide action. Erythropoietic growth factors and immunomodulatory drugs are recognized to variably increase thrombotic potential. Indeed, when combined with dexamethasone or other antineoplastics, thrombo-embolic complications have been reported in up to 10-15% of non-prophylaxed patients with multiple myeloma (13,14). The thrombotic potential of lenalidomide appears much lower than thalidomide despite greater pharmacologic activity. In two recently completed phase III trials involving 692 patients with relapsed multiple myeloma, [MM-009, and MM-010] thrombotic events were reported in 2.9% of patients assigned to treatment with dexamethasone and placebo, compared to 11.9 and 4.7% of patients in the lenalidomide and dexamethasone arms (15,16). Thrombo-embolic complications were not observed in patients receiving aspirin prophylaxis. Thrombo-embolic events were reported in 15 (3.4%) of the 408 MDS patients treated on the MDS-001, -002, and -003 trials. Among 873 patients with non-myeloid malignancy enrolled in 7 darbepoetin alfa (DA) registrational trials, thrombo-embolic events were reported in 7% of patients treated with DA, compared to 5.2% of patients

receiving epoetin alfa and 4.1% of placebo (17-20). A multivariate analysis identified DA treatment, prior TE history and poor ECOG performance status to be significant predictors of thrombo-embolic (ref. Data on File, Amgen 003). For this reason, candidates with a history of thrombo-embolic events within 3 years of registration will be excluded from study participation. Although epoetin alfa appeared less thrombogenic, thrombo-embolic events will be monitored in this study with an interim safety analysis of event frequency planned after 30 patients have completed 16 weeks of combined therapy on both arms of the study. Since platelet dysfunction is common in MDS and thrombocytopenia is a frequent adverse effect of CC-5013, aspirin prophylaxis will not be applied to this study.

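### Section 9.4.1 gives a one-arm stopping probability (0.12) as the probability of terminating the study; with either arm able to stop accrual, the study-level figure is 0.22

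*Combined protocol and SAP*

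**What the plan says.** Section 9.4.1 judges each regimen separately. A regimen is tolerable if its grade 3 or higher thrombo-embolic (TE) rate is 1% or less and its rate of other grade 3 or higher related toxicity is 30% or less. It is intolerable at 10% and 50% respectively. Hematologic toxicity is left out of the rule.

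The rule opens with "If, in the first 30 patients treated in Arm A or Arm B" and stops accrual to the study on "2 or more patients with grade 3 or higher thrombo-embolic events", or on 13 or more patients with other related grade 3 or higher toxicity. If the rule is not met "after the first 30 patients in arm B, additional 9 patients on arm B will be closely monitored".

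Assuming that the two toxicity types are independent, the section states that "the probability of terminating the study early is 0.12" when the true rates are 1% and 30%. It gives a probability of at least 0.83 when the TE rate is 10% or the other-toxicity rate is 50%. It does not mention combining the two arms.

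Section 1.3 gives background: "Thrombo-embolic events were reported in 15 (3.4%) of the 408 MDS patients" in three lenalidomide trials. It states neither the grade of these events nor the time over which they were counted.

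**The concern.** The rule acts on the study, and either arm can trigger it. The probability attached to it should therefore allow for two chances to stop. The only independence assumption in the text is between toxicity types, which suggests that the calculation was done for one arm and then described as a property of the study.

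What is at stake is how the rule is understood. The monitoring committee and the investigators are told that two tolerable regimens would lead to closure about one time in eight. If the true figure is nearer one in five, a trigger is weaker evidence of excess toxicity than the section implies.

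**Working it through.** **Inputs, all from Section 9.4.1.** n = 30 per arm; TE cut-off 2; other-toxicity cut-off 13; tolerable rates 1% and 30%; intolerable rates 10% and 50%; independence of the two toxicity types. One assumption is added: patients in the two arms are independent of each other.

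**Step 1. Reproduce the stated figure (one arm, exact binomial tails).**

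- P(TE >= 2 | n = 30, 1%) = 1 - 0.99^30 - 30(0.01)(0.99^29) = 0.0361
- P(other >= 13 | n = 30, 30%) = 0.0845
- One arm triggers: 1 - (1 - 0.0361)(1 - 0.0845) = 0.1176, which rounds to the stated 0.12.

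**Step 2. Reproduce the second figure (one arm).**

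- TE 10%, other 30%: P(TE >= 2) = 0.8163, so 1 - (1 - 0.8163)(1 - 0.0845) = 0.832
- TE 1%, other 50%: P(other >= 13) = 0.8192, so 1 - (1 - 0.0361)(1 - 0.8192) = 0.826

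Both round to 0.83. The two stated figures are therefore one-arm figures.

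**Step 3. Study level.** P(study stops) = 1 - (1 - p_A)(1 - p_B), where p_A and p_B are the one-arm probabilities.

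| True rates | One arm | Study |
|---|---|---|
| Both arms tolerable (TE 1%, other 30%) | 0.118 | 1 - (1 - 0.1176)^2 = 0.221 |
| One arm TE 10%, other arm tolerable | 0.832 (toxic arm) | 0.852 |
| One arm other toxicity 50%, other arm tolerable | 0.826 (toxic arm) | 0.846 |
| Both arms TE 10%, other 30% | 0.832 | 0.972 |
| Both arms TE 1%, other 50% | 0.826 | 0.970 |

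**Step 4. Conditional sensitivity to the TE rate (same rates in both arms).**

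| TE rate (grade 3 or higher) | Other toxicity | Study |
|---|---|---|
| 1% | 20% | 0.077 |
| 1% | 30% | 0.22 |
| 2% | 30% | 0.35 |
| 3.4% | 20% | 0.47 |
| 3.4% | 30% | 0.56 |

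With other toxicity at 30%, the study figure reaches 0.5 at a TE rate of about 3.0%. The printed 3.4% is itself slightly off, since 15/408 = 3.7%. At 3.7% the last two rows become 0.52 and 0.59.

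**The case against.** **Thirty patients in total.** The rule's opening words could mean 30 patients across both arms, and then 0.12 would be a study figure. The rest of the section does not fit this reading. It judges each regimen, and it speaks of 30 patients in Arm B alone before 9 more are followed. Nor does pooling 60 patients under the same cut-offs explain 0.12, because it gives 0.95. If 30 in total was meant, the text needs to say so.

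**A corner value.** The 0.22 places both arms at both tolerable limits, and it falls to 0.077 with other toxicity at 20%. This is correct, but 0.12 is quoted at the same corner, so the comparison is like for like.

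**The 0.83 is not wrong.** This stands. As a lower bound it also holds for the study, provided that the remaining rates sit at their tolerable limits. It needs only a label.

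**Little consequence now.** The boundary and the primary analysis are unaffected, and the understated risk is of stopping too readily. Section 9 reports 29 and 28 patients randomized by September 2010, while Section 5.4 carries a 2019 risk list, so the 30-patient review was probably long past. This lowers the urgency. The stated property of the rule is still incorrect.

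**Stronger readings that the documents do not support.**

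- A reader might infer from the 3.4% in Section 1.3 that the rule would more likely than not close a study of drugs behaving as expected. That needs nearly all the reported events to be grade 3 or higher and to fall within the period counted, with other toxicity at its 30% limit in both arms. If 75% of the events were grade 3 or higher, the figure would be 0.43 to 0.46; if half were, 0.31 to 0.33. Section 1.2 describes non-hematologic effects in the first lenalidomide trial as infrequent and mild to moderate.
- The 5.2% TE rate for epoetin alfa in Section 1.3 comes from non-myeloid malignancy, so it is not an expected rate for Arm B. The pilot in Section 1.2 reported no such events on the combination, although only 18 patients went on to it.
- Section 9.4 says that "All interim analyses will be performed on patients randomized before May 19, 2010 and after September 24", which might seem to remove 7 treated Arm B patients from the safety count. The opening of Section 9 ties that exclusion to the primary endpoint. Even read literally, later patients would fill the 30 places and the stopping probability would not change.
- Section 1.3 places a safety analysis of TE frequency "planned after 30 patients have completed 16 weeks of combined therapy on both arms", a timing that Section 9.4.1 does not repeat. That is loose wording to reconcile; it does not show a second, conflicting threshold.

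**Conclusion.** The stated 0.12 is wrong as a study-level probability. It is the one-arm value (0.1176); the study-level value at the same rates is 0.22, an absolute difference of about 0.10. This rests on 30 patients per arm, both arms at the tolerable limits, independence of the arms, and the plan's own independence of the two toxicity types.

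The 0.83 is also a one-arm value, but its lower bound survives: 0.85 with one toxic arm and 0.97 with two. Stopping probabilities at higher TE rates are a conditional sensitivity only, because the documents give no grade 3 or higher TE rate for either regimen.

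**What to change.** In Section 9.4.1, restate the tolerable case as 0.12 per arm and 0.22 for the study (either arm). Label 0.83 as the per-arm figure and add the study-level values: 0.85 if one arm is toxic, 0.97 if both are. State that the rule is applied to the first 30 patients in each arm.

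Optionally, add the study-level probability at higher TE rates with other toxicity at 30% in both arms: 0.35 at 2% and 0.56 at 3.4%. Note alongside that the 3.4% in Section 1.3 has no grade or time window, and that 0.56 falls to 0.47 if other toxicity is 20%. Two small clarifications could go in at the same time: align the timing in Section 1.3 with Section 9.4.1, and say whether the exclusion of 14 patients applies to toxicity monitoring.

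The cost is wording only. The cut-offs, sample size and analyses stay as they are. The price is a less favourable stated probability of stopping a tolerable study.
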